We want to test if computers trained to spot urgent and emergency forms (Artificial Intelligence or 'Al') can reduce these delays. We also want to know if Al works in the same way for all patients and whether it is good value for money.

What will we do?

We will study an AI system that is already used in NHS GP practices. We will give it to 20 GP practices not currently using it. We will measure the delays for patients receiving urgent and emergency help for 12 months before and after they start using the AI. We will compare this to 20 other GP practices that will not use the AI. We will also measure whether the AI affects staff workload and whether it works in the same way for patients from different backgrounds.

What difference will we make?

If the AI reduces care delays, patients who need urgent and emergency help will receive it sooner. We will help the NHS and companies that make online consultation systems decide whether they should use AI. We will help members of the public and GP practices understand what AI is and how they can use it to benefit both patients and staff.

3) SCIENTIFIC SUMMARY

[figure not shown]
Background

Online consultations allow patients to contact their GP practice about their health problems using an online form. Currently, 94% of GP practices in England use online consultations. PATCHS is an online consultation system launched in 2020 by commercial company Spectra Analytics. Approximately 1000 (~20%) GP practices in England currently use PATCHS.

A risk of online consultations is that patients submit forms describing medical emergencies that are not recognised quickly enough by their GP practice. To address this, Spectra Analytics developed artificial intelligence triage (AI Triage) within PATCHS to alert patients and GP practice staff when a patient describes a health problem that may suggest they require urgent or emergency treatment.

PATCHS AI Triage is a Class I (low risk) medical device and has been registered with the MHRA since October 2021. It has NHS approval for use in clinical practice and meets NHS DCB0129 safety standards. The intended purpose of PATCHS AI Triage is to assist patients and GP practice staff in making triage decisions, not to replace human judgment. During this project, PATCHS AI Triage will continue to be used within the scope of its intended purpose.

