consultation e.g. health problem or administrative. When the form is submitted by the patient it enters an inbox, where GP practice staff can prioritise and respond to online consultations. Patients complete forms in PATCHS by describing their queries in unstructured free text in response to open-ended questions in the system that mimic a typical primary care consultation, as opposed to multiple choice questionnaires. Most (65%) online consultation systems allow patients to describe their queries using unstructured free text [7].

In addition to their query, patients enter their details including sex, ethnicity, home address, email address, and telephone number. Receptionists typically review incoming PATCHS online consultations first, and will deal with any queries they can, and assign those they cannot to other staff within PATCHS, including clinicians, if it requires their input. Patients are then contacted to resolve their query – either by written message or video consultation within PATCHS, telephone or by arranging an in-person appointment. GP practices can assign PATCHS online consultations to future dates to be dealt with by clinicians if deemed necessary to match staffing capacity.

When GP practice staff process patients' online consultations in PATCHS, they record various triage decisions (Appendix 1, Screenshot 1), which have been developed based on qualitative research and workshops conducted with 22 GP practice staff and 37 patients. These triage decisions include whether they believe the online consultation is either:

[figure not shown]
- **Emergency**: patient could be harmed if not resolved within 24 hours and may require immediate care from emergency services.
- **Urgent**: the patient could be harmed if not resolved within the next 48 hours.
- Routine: neither urgent nor emergency.

Analysis of 122,504 PATCHS online consultations submitted to 80 GP practices show that 7922 (6.5%) are urgent or emergency, 25% of which on average are not resolved in the above timelines. We define these as delays in urgent and emergency care: online consultations deemed urgent or emergency by GP practice staff where the difference between the time it was submitted by a patient or their carer in PATCHS and the time it was completed by a staff member is longer than 48 or 24 hours, respectively.

PATCHS AI Triage: development and validation

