To attempt to reduce these delays in urgent and emergency care, Spectra Analytics developed an Al Triage add-on system for the standard PATCHS product (called 'PATCHS Al Triage' for this document) in project IRAS ID: 264891. PATCHS Al Triage uses natural language processing (NLP) and deep learning to analyse online consultations to predict whether they are either urgent, emergency, or routine based on the above definitions.

PATCHS AI Triage was initially developed in 2020 using 43,998 online consultations for 37,000 patients to 52 GP practices using PATCHS. The unstructured free-text written by patients in their online consultation, type of online consultation submitted (e.g. new health problem, administrative query), and patient demographics were used as inputs to the model. The manually applied 'urgent' and 'emergency' flags from GP practice staff were used as model outputs. Data were split into training (90%) and test (10%) datasets. AI model training was optimised for a high true positive rate based on findings from co-design workshops where GP practice staff and patients felt it was most important that AI Triage systems missed as few urgent or emergency online consultations as possible. The true positive rate of PATCHS AI Triage to detect urgent and emergency online consultations was 86% in the training dataset and 84% in the test dataset. Subsequently in 2021, PATCHS AI Triage was evaluated in 14 early adopter GP practices covering inner city and urban areas in the north and south of England. Using triage decisions made by GP practice

staff to define urgent and emergency online consultations, its true positive rate was 94% in 19,805 online consultations previously unseen by the AI prospectively for 9,725 patients (21% non-white). Qualitative research with 20 staff at early adopter practices showed they found PATCHS AI Triage both acceptable and useful. Work is currently underway to re-train PATCHS AI Triage to ensure its performance has been maintained over time, and scientific publications reporting its development and validation are being prepared for peer-review.

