We will calculate the overall accuracy (proportion of 'correct' predictions), true positive rate, true negative rate, positive predictive value, and negative predictive value of AI Triage in intervention practices. Our primary measure of accuracy will be for urgent and emergency online consultations combined; secondary measures will assess urgent and emergency online consultations separately. There is no gold standard test to decide the 'correct' triage decision for online consultations written by patients in their own words. We will therefore use the triage decisions made by GP practice staff when processing online consultations and consider their triage decision as 'correct'. Where AI Triage predicts an online consultation as 'urgent' or 'emergency' we will consider it a:

- **True positive** if the triage decision is not changed by staff, or if staff change the triage decision and the highest triage decision applied by staff is 'urgent' or 'emergency'.
- False positive if staff change the triage decision and the highest triage decision applied by staff is
 'routine'.

Where AI Triage predicts an online consultation as 'routine', we will consider it a:

- **True negative** if the triage decision is not changed by staff, or if staff change the triage decision and the highest triage decision applied by staff is 'routine'.
- False negative if staff change the triage decision and the highest triage decision applied by staff is 'urgent' or 'emergency'.

We will quantify cases where emergency online consultations have been predicted as 'routine' as these represent the highest risk misclassifications. The Spectra Analytics Clinical Safety team will investigate these and other patient safety incidents reported by GP practices as per their internal processes to comply with MHRA and NHS DCB0129 standards (16). We will review their findings to understand if there are patient groups or online consultation topics that are at higher risk of misclassification by Al Triage.

Potential triage behaviour change in control GP practices

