Similar to the interrupted time series analysis, limitations with the above approach include that: staff triage decisions could be applied by non-clinicians; the true urgency of an online consultation may only be apparent when further information has been obtained from the patient (e.g. over the telephone); we assume AI Triage predictions for patients who receive a signpost message and cancel their online consultation is correct. We will therefore conduct sensitivity analyses where: we restrict triage decisions to those only made by clinicians; the final triage decision when the online consultation is resolved is used; patients who receive a signpost message and cancel their online consultation are excluded. As mentioned above, multiple online consultations from the same patient are expected to be infrequent, though will be assessed by using a patient-level variable in models and by re-running analyses after randomly sampling one online consultation per patient.

Health inequalities

We will assess the potential influence of AI Triage on health inequalities across different age groups, sexes, ethnic backgrounds, Index of Multiple Deprivation quintiles, and non-English language usage. In dose and reach metrics we will compare the proportion of each sub-group in the population using online consultations in intervention and control practices in the pre- and intervention periods (44), and to the characteristics of the wider practice populations in National General Practice Profiles (38).

Each accuracy metric will be tested for differences in performance between patient sub-groups. We will also undertake a failure case analysis to explore factors why AI Triage may have predicted incorrectly (46)

by comparing the characteristics of patients who have submitted online consultations classified as false positive and negatives to those of true positive and negative predictions ('error auditing') (47). Additional factors to test will include those related to the online consultation (including type of online consultation, time and day of submission), GP practice staff who applied the triage decision (including role, experience using PATCHS), and GP practice (including size, geographic location, experience using PATCHS).

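### Sub-group tests of PPV and NPV are read as tests of AI performance, but both also move with each sub-group's prevalence of urgent and emergency forms

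*Protocol*

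**What the plan says.** In section 11.1, under AI Triage accuracy in intervention GP practices, the protocol sets five metrics: overall accuracy and the "true positive rate, true negative rate, positive predictive value, and negative predictive value of" AI Triage. The reference is the staff triage decision, and a prediction that staff leave unchanged counts as correct.

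The Health inequalities paragraph of the process evaluation looks at AI Triage "across different age groups, sexes, ethnic backgrounds, Index of Multiple Deprivation quintiles, and non-English language usage", and then says: "Each accuracy metric will be tested for differences in performance between patient sub-groups". All five metrics are tested, a difference is described as one of performance, and no metric takes priority.

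Prevalence of urgent and emergency forms appears elsewhere: in matching the arms (section 8.4) and in sub-sampling for the time-series sensitivity analyses (section 11.1). It is not brought into these sub-group tests. The tests serve research question 10 on health inequalities and the promise in the plain-language summary to measure "whether it works in the same way for patients from different backgrounds".

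**The concern.** TPR and TNR condition on the reference decision. PPV and NPV condition on the prediction, so they mix the AI's error rates with the share of forms in the sub-group that are urgent or emergency. Suppose two sub-groups have the same TPR and TNR but different prevalence. Their PPV and NPV must then differ, unless the AI is perfect or uninformative. A test of equal PPV will pick up that difference in case mix, and the protocol's wording would report it as a difference in AI performance.

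At stake is the answer to research question 10. The study could report that the AI works less well for a patient group when only the prevalence differs. If the PPV and TPR tests disagree, the plan does not say which one answers the question.

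**Working it through.** **Inputs from the protocol**
- Overall prevalence (section 5): the earlier data "show that 7922 (6.5%) are urgent or emergency". Check: 7922 / 122,504 = 6.47%, which agrees.
- Volume (section 11.2): 50 urgent and emergency forms per practice per month, 12 months, 20 intervention practices. 20 x 50 x 12 = 12,000; 12,000 / 0.065 = about 184,600 forms.
- TPR (section 5): "its true positive rate was 94% in 19,805 online consultations previously unseen by the AI". In development it "was 86% in the training dataset and 84% in the test dataset".
- Sub-group share: 21%, the non-white share in the early adopter evaluation (section 5), used as an example.

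The only related sample size is the 2928 for the primary outcome. It reproduces exactly: 25% v 20%, two-sided 5% alpha, 90% power and no continuity correction give 1464 per group, 2928 in total. The protocol gives no figure for the sub-group accuracy tests.

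**Assumptions, because the protocol gives neither**
- TNR: 75% to 95%.
- Sub-group prevalence: 6% v 7%, or 5% v 8%.
- Test: two-sample proportion test at two-sided 5%, forms independent.

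**Formulas**, with p the prevalence:
- PPV = p·TPR / [p·TPR + (1−p)(1−TNR)]
- NPV = (1−p)·TNR / [(1−p)·TNR + p(1−TPR)]
- Accuracy = p·TPR + (1−p)·TNR, so a gap in p moves accuracy by that gap times (TPR − TNR)

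**Same AI in both groups: TPR 94%, TNR 85%**
- p = 5%: PPV = 0.047 / (0.047 + 0.1425) = 24.8%; NPV = 0.8075 / 0.8105 = 99.63%; accuracy 85.45%.
- p = 8%: PPV = 0.0752 / (0.0752 + 0.138) = 35.3%; NPV = 0.782 / 0.7868 = 99.39%; accuracy 85.72%.

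**Size of the PPV test, 5% v 8%.** Let the 21% group (38,769 forms) have prevalence 8% and the rest (145,846) have 5%. Flagged forms: 38,769 x 0.2132 = 8,266 and 145,846 x 0.1895 = 27,638. Pooled PPV = 27.2%; SE = √[0.272 x 0.728 x (1/8,266 + 1/27,638)] = 0.0056; z = (0.353 − 0.248) / 0.0056 = about 18.8. Rejection is certain in practice.

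**Size of the NPV test, 6% v 7%.** The 21% group has 7%. Missed forms: 38,769 x 0.07 x 0.06 = 163 of 30,810 unflagged (0.529%). In the rest: 145,846 x 0.06 x 0.06 = 525 of 117,056 (0.449%). SE = 0.000436, z = 1.84, so the chance of exceeding 1.96 is about 45%.

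**Simulated rejection rates** (4,000 runs each, TPR 94% and TNR identical in both groups):

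| Sub-group share | Prevalence | TNR | PPV | NPV |
|---|---|---|---|---|
| 21% | 5% v 8% | 75-95% | 100% | at least 99.9% |
| 21% | 6% v 7% | 75-95% | at least 99.7% | 42-45% |
| 5% | 6% v 7% | 75-95% | 74-93% | 18% |
| 2% | 6% v 7% | 80% | 60% | 12% |

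The TPR and TNR tests stay near 5% throughout. With equal prevalence (6.5% in both groups), all five tests reject at about 5%, so prevalence alone drives the excess.

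**Overall accuracy** at 5% v 8% with a 50:50 split rejects in 93% of runs at TNR 0.70, 64% at 0.80, 12.5% at 0.90, and 5% at 0.94, where TNR equals TPR.

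**The case against.** Several points on the other side stand.

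- **The effect is conditional.** A reader might infer that these tests reject whatever the data. They do not: at equal prevalence they hold 5%, and the protocol reports no prevalence by sub-group. But equal prevalence in every age band, deprivation quintile, ethnic group and language group is the stronger assumption, and a one-point gap is enough for PPV in a group of moderate size.
- **Overall accuracy is not affected like PPV and NPV.** It moves only with TPR minus TNR, and no TNR is reported. To call three of the five metrics equally misleading would go too far.
- **Masking is largely covered.** A reader might infer that a group with a worse TPR could pass as equal. With TPR 84% v 94% and prevalence 2.5% v 6.5%, the NPV test rejects only 4-6% of the time, but the TPR test, which is also planned, rejects at least 99.8%. The failure case analysis adds a second look.
- **PPV and NPV matter in themselves.** A lower PPV means more false flags for those patients, whatever the cause. This is a reason to report them, not to call the gap AI performance.
- **TPR and TNR are not clean here.** Section 7.2 has the AI pre-populate the triage decision, and unchanged predictions count as correct. Suppose staff uphold 90% of flags and 99% of routine predictions in both groups, with flag rates of 10% and 15%. PPV and NPV are then equal, yet TPR = 0.090 / (0.090 + 0.009) = 90.9% v 0.135 / (0.135 + 0.0085) = 94.1%. A rule to test TPR and TNR only, with no caveat, would not be safe.
- **The form of test is open.** The protocol names none, and clustering would change the exact rates. With a crude design effect of 10, z in the PPV example is still 18.8 / √10 = 5.9. Test form and adjustment may fairly be left to the SAP. Reading every metric as performance is fixed in the protocol.

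**Conclusion.** The point holds in conditional form. The protocol tests PPV and NPV between patient sub-groups as measures of AI performance and takes no account of sub-group prevalence. If prevalence differs by 1 to 3 percentage points, the PPV test, and often the NPV test, will reject at this study's volume with identical TPR and TNR. Rates fall in small sub-groups. Overall accuracy is affected only as far as TPR and TNR differ.

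The size rests on assumed prevalence gaps, an assumed TNR of 75-95% and independent forms; the dependence on prevalence is algebra. The documents do not show that any sub-group gap exists, nor that a worse TPR would go unseen. The matter is confined to the process evaluation and research question 10. The primary outcome is not affected.

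**What to change.** In the Health inequalities paragraph of the process evaluation:

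1. Base the conclusion about differential AI performance on TPR and TNR, as differences with 95% confidence intervals.
2. Keep PPV, NPV and overall accuracy by sub-group. Show them beside that sub-group's prevalence and AI flag rate, or standardise them by putting a common prevalence into the formulas above. State that raw differences in them are not by themselves evidence of unequal AI performance.
3. State that TPR and TNR in intervention practices are not independent of the AI, because unchanged predictions count as correct. Repeat the TPR and TNR sub-group comparison in control practices, where section 11.1 already obtains predictions that staff do not see.

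The cost is a few sentences. All the data are already planned for, no metric is dropped, and the sample size and primary analysis do not change.

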16.1 Approvals

NHS Research Ethics Committee and Health Research Authority approval will be obtained before commencing research. Submission to the MHRA is not required for this study because the intervention is a UKCA-marked medical device already used in routine clinical practice and will be used within the scope of its intended purpose. The study will be conducted in full conformance with all relevant legal requirements and the principles of the Declaration of Helsinki, Good Clinical Practice and the UK Policy Framework for Health and Social Care Research 2017.

16.2 Risks

Risks to participants

This study uses routinely collected data to evaluate a UKCA-marked medical device already used in routine clinical practice. Consequently, risks for participants are minimal. The only risk we have identified related to study procedures is the risk of identifying participants from the research data. A formal risk assessment (Appendix 2) based on guidance from the Information Commissioner's Office (35) has been undertaken as described above. It concludes the data are effectively anonymised and the risk of a motivated intruder identifying a participant is low. Security arrangements for protecting the data include: 1) Using industry standard practices for transferring data as password-protected files using Hypertext Transfer Protocol Secure over a Transport Layer Security connection encrypted both in transit and at rest, 2) Storing the data on secure UoM Research Data Storage servers.

Risks to researchers

Researchers will analyse routinely collected data only. We have identified no additional risks to them in conducting the study.

16.3 Benefits

[figure not shown]
There may be benefits associated with using AI Triage that impact delays in urgent and emergency primary care, staff workload, and health inequalities. GP practices in the study (both intervention and control) will be offered the intervention before GP practices outside the study; they and their patients may therefore experience these benefits sooner.

17) STATEMENT OF INDEMNITY

The University has insurance available regarding research involving human subjects that provides cover for legal liabilities arising from its actions or those of its staff or supervised students. The University also has insurance available that provides compensation for non-negligent harm to research subjects occasioned in circumstances that are under the control of the University.

18) FUNDING AND RESOURCES

This project is funded by the NIHR HSDR programme, reference number NIHR153121.

19) PUBLICATION POLICY

This research protocol will be publicly registered on the ISRCTN (International Standard Randomised Controlled Trial Number) registry (51). Findings will be published in open-access peer-reviewed scientific journals. Analysis code will be made available. We will also produce short evidence summaries communicating key findings in an accessible way, which will be hosted on publicly available websites (e.g. www.patchs.ai) and disseminated to participating GP practices and patients by Spectra Analytics via email. GP practices will be encouraged to share these findings with their patients, for example by publishing them on their website.

20) DECLARATION OF INTERESTS

[name] is a part-time employee of Spectra Analytics as Chief Medical Officer and is a shareholder in the company. Spectra Analytics develop the Al Triage intervention. Co-Investigators have no relevant interests to declare.

[figure not shown]
21) REFERENCES

- NHS Digital [Internet]. [cited 2023 Dec 13]. Appointments in General Practice. Available from: https://digital.nhs.uk/data-and-information/publications/statistical/appointments-in-general-practice
